12.4.5 Breaking the Blind

A set of tamper-proof sealed individual envelopes containing the bottle numbers on the outside of the envelope and the treatment code inside the envelope, will be sent to the investigative site. In the event of a medical emergency that necessitates breaking the code, the sealed envelope containing the treatment code may be opened. The seal will only be broken by the Investigator in the event of an emergency for which knowledge of the subject's double-blind investigational product will have a direct impact on treatment decisions. Every effort will be made to discuss the decision to break the blind with the Cetylite Medical Monitor in advance.

When the blind is broken, the Investigator will notify the Sponsor's Medical Monitor immediately in order to document the reason and date of the unblinding. The event will also be recorded on the CRF and in the source document. The Investigator will submit a written explanation to the Sponsor describing the event within 5 business days.

12.4.6 Discontinuation of Study due to an SAE

The study will be discontinued for safety reasons if a serious adverse event occurs in one subject unless it is demonstrated that the serious adverse event is not related (as defined in section 12.4.1 of this protocol) to study drug, in which case the study will not be required to stop.

The IRB will be notified within 24 hours of any event that results in discontinuation of the study.

13. STATISTICAL METHODS AND DATA HANDLING

The Statistics Group will perform statistical analyses of efficacy data. All computations will be performed using SAS® version 9.1 or higher (SAS Institute, Cary, NC). Statistical significance will be declared if the p-value is ≤ 0.05 .

Descriptive statistics for numerical variables will include n (number of subjects involved), mean, standard deviation, median, minimum, and maximum values. Categorical variables will be described by number and percent.

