Irritation and/or infection at the site of application will be assessed. The severity, relationship to treatment, action taken, and outcome of the events will be documented. The incidence of all adverse events and drug-related adverse events will be evaluated. In the event of any health related emergency, the clinical site will have a trained medical staff with a fully equipped emergency crash cart.

STATISTICAL ANALYSIS:

Primary Efficacy Endpoints:

- Duration of anesthesia as measured by PPT for one spray CTY-5339-A compared to the one spray CTY-5339-CB
- Duration of anesthesia as measured by QST Heat for one spray CTY-5339-A compared to the one spray CTY-5339-CB

Secondary Efficacy Endpoints:

- Duration of anesthesia as measured by PPT and QST Heat for the two spray CTY-5339-A compared to the one spray CTY-5339-CB plus one spray CTY-5339-P
- Duration of anesthesia as measured by PPT and QST Heat for the two spray CTY-5339-A compared to the one spray CTY-5339-A
- Onset of anesthesia for PPT and QST Heat
- Percentage of responders for PPT and QST Heat for both onset and duration
- Percentage of responders for PPT and QST Heat at each time point

Safety Data:

- SBP, DBP, and HR at Baseline and at the end of each 60-minute test session,
- Pulse oximetry at Baseline and at 10, 20, 30, 40, 50 and 60 minutes after drug administration,
- 12 Lead ECG at Baseline and at the end of each 60-minute test session,
- Methemoglobinemia at Baseline and at the end of each 60-minute test session, and
- Analysis of incidence and severity of all adverse events

For the PPT, a “Responder” is defined based on an assessment of “No Pain” or “Less Pain” in response to the pain stimulus at each observation time when compared to the non-treated site, (See Appendix 2). The % of responders at each time point will be compared between treatments. In addition, the % of subjects who have Onset (and Duration) will also be compared between treatments.

For the QST, a “Responder” is defined as follows: If the average heat

temperature at each time point is greater than the average heat temperature at Baseline, then the subject at that time point will be considered a “Responder”. The % of responders at each time point will be compared between treatments. In addition, the % of subjects who have Onset (and Duration) will also be compared between treatments.

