8.3.2 Secondary Outcome Measures

- Duration of anesthesia as measured by PPT and QST Heat for the two sprays of CTY-5339-A compared to the one spray of CTY-5339-CB plus one spray of CTY-5339-P

- Duration of anesthesia as measured by PPT and QST Heat for the two sprays of CTY-5339-A compared to the one spray of CTY-5339-A
- Onset of anesthesia for PPT and QST Heat
- Percentage of responders for PPT and QST Heat for both onset and duration
- Percentage of responders for PPT and QST Heat at each time point

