8.4 Hypothesis

The following hypotheses will be tested to analyze the primary outcomes of the study:

- The null hypothesis that the duration of anesthesia (PPT and QST Heat) for the one spray CTY-5339-A group is the same as the corresponding duration for the CTY-5339-CB one spray group will be tested against the alternative hypothesis that the means are not equal.

The following hypotheses will be tested to analyze the secondary outcomes of the study:

- The null hypothesis that the duration of anesthesia (PPT and QST Heat) for the two spray CTY-5339-A group is the same as the corresponding duration for the CTY-5339-CB one spray plus CTY-5339-P one spray group will be tested against the alternative hypothesis that the means are not equal.
- The null hypothesis that the onset of anesthesia (PPT and QST Heat) for the CTY-5339-A groups is equal to the corresponding onset for CTY-5339-CB group will be tested against the alternative hypothesis that the means are not equal.
- The null hypothesis that the onset time until the first responder event (PPT and QST Heat) for the CTY-5339-A groups is equal to the corresponding onset time until a first responder event for CTY-5339-CB group will be tested against the alternative hypothesis that the event times are not equal.
- The null hypothesis that the duration time until the first non-responder event (QST and PPT) for the CTY-5339-A groups is equal to the corresponding duration time until the first non-responder event for CTY-5339-CB group will be tested against the alternative hypothesis that the event times are not equal.

The predicted outcome is that CTY-5339-A when locally applied to cheek mucosal tissue in the mouth will have an onset comparable to the fastest constituent, benzocaine, and a prolonged effect comparable to the longest acting constituent, tetracaine, of the combination product. The study also is designed to demonstrate that both the CTY-5339-A one and two-spray dosages are safe. (The assumption is made that benzocaine has a faster onset of action than tetracaine HCl.)

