13.5 Statistical Methods for Efficacy Evaluations

The primary efficacy analyses will be based on Modified Intent-to-Treat Population. The key comparisons will include:

1. CTY-5339-A, one spray versus CTY-5339-CB, one spray

The co-primary efficacy variables are duration of effect as measured by PPT and QST Heat. Duration of effect is defined as the time (in minutes) from onset to treatment failure (*i.e.*, for PPT, an assessment of “Same/More” pain, and for QST, the average heat temperature is greater than the average heat temperature at Baseline (non-treated cheek), up to the 60-minute time point (at two consecutive time points). For those discontinuing from the study for any other reason, the time to treatment failure will be censored at the last assessment time.

The secondary efficacy variables include:

- Duration of effect (PPT and QST) for CTY-5339A two sprays versus CTY-5339-CB, one spray plus CTY-5339-P one spray

- Duration of effect (PPT and QST) for CTY-5339A two sprays versus CTY-5339-A one spray
- Onset of anesthesia in minutes for PPT and QST Heat
- Percentage of responders at each time point for PPT and QST Heat for both onset and duration

Continuous variables will be analyzed via an ANOVA model with treatment effects at each of assessed time points. Pairwise comparisons for variables related to percentages will be analyzed via chi square tests. The 95% confidence intervals of the treatment differences will be presented using normal approximation with continuity correction, if appropriate. Pairwise comparisons for time-to-event related variables will be analyzed via a log rank model with treatment effects. Median time to event will be estimated and the 95% confidence intervals for the median will be presented, if appropriate.

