13.6 Multiple End Points and Multiple Comparisons

Duration of Effect, as assessed by PPT and QST Heat are co-primary efficacy parameters. In order to control the overall significance level for the two primary endpoints, the total alpha level of 0.1 is Bonferroni adjusted to $0.10/2 = 0.05$ (since this is a proof of concept study, the total alpha level of 0.1 instead of 0.05 has been selected). The study will be considered successful if either of the two primary endpoints is statistically significant.

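### Section 13 allows significance to be declared at p ≤ 0.05 for every efficacy test, but Section 13.6 controls error only for the two primary duration tests

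*Combined protocol and SAP*

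**What the plan says.** - **Threshold.** The opening of Section 13, which introduces the efficacy analyses, states: "Statistical significance will be declared if the p-value is ≤ 0.05". No endpoint is excepted.
- **Multiplicity.** Section 13.6 is the only section on the subject. Its adjustment is made "In order to control the overall significance level for the two primary endpoints": a total of 0.10 is split into 0.05 for PPT duration and 0.05 for QST duration. It adds: "The study will be considered successful if either of the two primary endpoints is statistically significant". Secondary endpoints are not mentioned.
- **Secondary endpoints are planned as tests.** Section 8.4 gives formal null hypotheses for secondary outcomes, each of the form that the null "will be tested against the alternative hypothesis that the means are not equal" or the equivalent for event times. Section 8.3.2 lists "Percentage of responders for PPT and QST Heat at each time point". The synopsis says for both PPT and QST: "The % of responders at each time point will be compared between treatments". Section 13.5 supplies the method: "Pairwise comparisons for variables related to percentages will be analyzed via chi square tests".
- **No hierarchy, adjustment or nominal label** for these tests appears anywhere in the document.

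**The concern.** Read literally, the plan commits the report to declaring significance for dozens of secondary comparisons with no limit on the overall chance of a false declaration. The responder percentages are the largest group because they are repeated at every assessment time.

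Results at adjacent times come from the same subjects a few minutes apart, so chance findings tend to arrive in runs. A run of significant time points can look like a sustained effect.

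The same gap covers the two-spray duration comparisons. These are secondary, yet Section 13.1 says the study is to find whether one or two sprays have a relevant advantage. As written, a two-spray result could be declared significant whatever happens to the primary tests.

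**Working it through.** **The plan's own figure.** 0.10 / 2 = 0.05 per primary test, as Section 13.6 states. The two add back to 0.10; if independent, the chance of at least one false positive is 1 − 0.95² = 0.0975. The primary arithmetic is correct.

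**Number of time points** (Section 4 flow chart, Section 9).
- PPT: 1, 2, 3, 4, 5, then 10 to 60 minutes by 5 = 16.
- QST: 5 to 60 minutes by 5 = 12.
- Total 28.

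**Number of contrasts.** The synopsis and the onset and responder-event hypotheses in Section 8.4 compare CTY-5339-A groups with CTY-5339-CB: two contrasts. Two sprays against one spray of CTY-5339-A is listed in Sections 8.3.2 and 13.5 for duration only; extending it to responders is an inference.
- Two contrasts: 28 × 2 = 56 tests.
- Three contrasts: 28 × 3 = 84 tests.

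**Nominal expectation if all regimens are equal** (tests × 0.05; independence is not needed).
- 56 × 0.05 = 2.8.
- 84 × 0.05 = 4.2.

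The chance of at least one would be 1 − 0.95^56 = 0.943 or 1 − 0.95^84 = 0.987 under independence. These are upper guides, because neighbouring times are correlated.

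**Effect of the planned test.** Each subject receives one CTY-5339-A regimen and CTY-5339-CB in different sessions, so both contrasts with CTY-5339-CB are within subject. An ordinary chi-square takes the variance of the difference as 2p(1 − p)/n. With within-subject correlation ρ the true variance is 2p(1 − p)(1 − ρ)/n, so the true size is 2Φ(−1.96/√(1 − ρ)). The documents give no value for ρ; the values below are assumptions. Two sprays against one spray compares different subjects and keeps size 0.05, contributing 28 × 0.05 = 1.40.

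| Assumed ρ | 1.96/√(1 − ρ) | True size, contrasts with CB | Expected, 56 tests | Expected, 84 tests |
|---|---|---|---|---|
| 0 | 1.960 | 0.050 | 2.80 | 4.20 |
| 0.33 | 2.394 | 0.0166 | 0.93 | 0.93 + 1.40 = 2.33 |
| 0.5 | 2.772 | 0.0056 | 0.31 | 0.31 + 1.40 = 1.71 |

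**Simulation check for 84 tests.** All regimens equal, 38 subjects per contrast arm, 3,000 trials per setting. Assumed log-normal onset (median 2 minutes) and end of effect (median 25 minutes), with within-subject correlation placed on the log end of effect.

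| Correlation | Mean false positives, uncorrected | At least one | Mean, continuity-corrected | At least one |
|---|---|---|---|---|
| 0 | 4.3 | 92% | 1.8 | 64% |
| 0.3 | 3.5 | 88% | 1.4 | 56% |
| 0.6 | 2.7 | 83% | 1.0 | 47% |

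Section 13.5 mentions a continuity correction for confidence intervals, not for the tests, so the uncorrected columns are closer to the text.

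**The case against.** The strongest reply is that this is a declared proof-of-concept study that openly accepts a total alpha of 0.10, and that uncontrolled secondary tests are common in such studies. Success depends on the primary tests alone, and Section 8.1 makes later studies conditional on success. That stands, and it limits the point to how secondary results are labelled. A reader might infer that secondary results drive the decision to proceed. The documents contain no such rule. The fallback in Section 13.1 is a clear trend in duration, not in responders at single time points.

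A reader might also infer that about four false results are almost certain. That goes too far, for three reasons. The third contrast is an inference. The planned test falls below 5% size on within-subject contrasts. And the calculation needs all regimens to be equal, whereas two sprays deliver 56 mg of benzocaine against 28 mg. If tetracaine adds nothing, two sprays may still differ from the other regimens, and a significant result there would not be false. Under that narrower premise only one spray against CTY-5339-CB is null: 28 tests, 28 × 0.05 = 1.4 nominally.

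Nor should QST temperature by time point be added as a further family of tests. Section 13.5 has a general sentence on ANOVA at each time point, but temperature is not a listed endpoint.

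None of this answers the textual gap: the rule says significance will be declared, and no passage exempts the secondary tests.

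**Conclusion.** The concern holds as a gap in scope. A general threshold of 0.05 applies to every efficacy test, and error is controlled for two of them. The responder comparisons by time point add 56 to 84 uncontrolled tests, depending on the contrasts intended.

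With all regimens equal and each test at its nominal size, 2.8 to 4.2 false declarations are expected. With the planned unpaired chi-square the figure is roughly 1 to 4 for 84 tests. If only the contrasts with CTY-5339-CB are tested it can fall below 1 once within-subject correlation is appreciable. The result depends on that correlation, on whether a continuity correction is used and on the number of contrasts, none of which the plan settles. Under any of these readings the false results would tend to sit at adjacent times.

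The primary tests and the success rule are not affected. What changes is which secondary results, including the two-spray duration comparisons, may be called significant.

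**What to change.** Amend the opening of Section 13 so that significance is declared only for the two primary tests under Section 13.6. State that all other secondary and per-time-point results will be given as estimates with nominal 95% confidence intervals, with any p-values labelled nominal. Say in Section 13.5 which contrasts apply to the responder percentages.

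If the sponsor wants confirmatory secondary claims, there is an optional addition. Test the two-spray duration contrasts in fixed order (against CTY-5339-CB plus vehicle, then against one spray of CTY-5339-A), separately within PPT and within QST. Each sequence runs at 0.05 and opens only if that modality's own primary test is met. This fits the either-endpoint success rule and keeps the total at 0.05 + 0.05 = 0.10.

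The cost is a wording amendment under Section 14.5, made before unblinding, with no new data or procedures. The downside is that fewer secondary results can be called significant.

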13.1 Sample Size Determination

This study is a proof-of-concept study to determine if CTY-5339-A one or two sprays have a relevant efficacy advantage over CTY-5339-CB. Although a statistically significant difference is desirable, a clear-cut trend for increased duration of analgesia would be acceptable. A sample of 76 subjects in the efficacy evaluation part was felt to be adequate for the purposes of this proof-of-concept study.

13.2 Analysis Populations

There will be three analysis populations:

Safety population: will include all randomized subjects who received the study medication. This population will be used for all safety summaries.

Intent-to-Treat (ITT) population: will include all randomized subjects who dosed with study medication and provided a Baseline assessment. All secondary efficacy analyses and summaries will be performed using this population.

Modified Intent-to-Treat (mITT) population: will include all randomized subjects who, as documented prior to the breaking of the study blind: (1) met all the inclusion and exclusion criteria and; (2) either completed the two 60 minute test sessions or returned to baseline values in all the evaluation tests. The primary efficacy analyses will be performed using this population.

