APPENDIX 1: DESCRIPTION OF TESTING METHODS

Appendix 1A: Pin Prick Test (PPT)

Oral Mucosa sensation directly over the circumscribed sites will be assessed with a 90-mm, 26-gauge pencil-point spinal needle (Polymedical; Temena S.A., Bondy, France or its equivalent) at Screening, Baseline and predetermined intervals after application of drug. To standardize the methodology, all tests are performed by holding the needle at its hub and orienting it perpendicular to the oral mucosa surface. Pressure is applied until the needle shaft bows slightly. At screening a numerical score on a 0 – 10 pain intensity scale (NRS) is recorded for each cheek. After study drug administration, subjects are instructed to rate the pinprick sensation perceived over the circumscribed treatment site compared to that perceived at the contra-lateral circumscribed, non-treated site and to report the sensation as none, less, or similar/more to the non-treated site. Reports of none or less indicate analgesia, while a report of similar/more indicates complete regression of analgesia. At each observation, 3 pin pricks are performed first on the non-treated side, and then on the treated side. For each cheek, the first pin prick will not be used for analysis. Of the remaining two pin pricks, the one with the most severe pain rating will be used for the data analysis.

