9. SUMMARY OF STUDY DESIGN

This is a single-dose, double-blind and single-center study with an active control treatment. All subjects will remain at the study center for each of the two 60 minute test sessions. The volunteer subjects will be tested at two different test sessions separated by 4-14 days and serve as their own control.

The study will include 76 subjects with 60-minute evaluations at each test session.

At each session, a circular area of approximately 1 inch in diameter will be isolated on one side of the cheek. Each session will use a different side of the cheek. The possible sequences of treatments at the two sessions are:

Session 1		Session 2	
Formulation	Sprays	Formulations	Sprays
CTY-5339-A	1	CTY-5339-CB	1
CTY-5339-A	2	CTY-5339-CB	1
CTY-5339-CB	1	CTY-5339-A	1
CTY-5339-CB	1	CTY-5339-A	2

(To maintain double-blind conditions, the CTY-5339-CB subjects in two spray sequences will also receive one spray with the vehicle control (CTY-5339-P) just outside the circumscribed area. A third party not involved with evaluating subjects will administer the drug.)

For PPT, evaluations will be done at 1-minute intervals following drug administration for the first 5 minutes to capture onset of anesthesia. Starting at 5 minutes after drug administration, both PPT and QST will be done at 5-minute intervals up to the one hour time point. Once onset has occurred, if there is no analgesia at two consecutive evaluation time points (from 10 minutes onward), the session will be discontinued. In addition, if onset of analgesia has not occurred by 10 minutes post dose, the subject will be considered a treatment failure and no further assessments will be made.

PPT: The PPT will be assessed, using a 90-mm, 26-gauge pencil-point spinal needle (Polymedic or equivalent; Temena S.A., Bondy, France or its equivalent). At each post dosing time point, PPT will be assessed in 3 repetitions on the non-treated site using a 0-10 Numerical Rating Scale (NRS) with "0" as no pain and "10" as severe pain. PPT will then be assessed in 3 repetitions on the treated site. These assessments will be compared to the contra-lateral, non-treated site as "No pain", "Less Pain" or "Similar/More Pain". "No Pain" or "Less Pain" at an application site will be recorded as presence of analgesia/anesthesia ("Responder").

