13.4 Data Adjustments and Derived Endpoints

13.4.1 Time Windows

Because some subjects may complete their assessments at times differing from the scheduled times, each such score will be adjusted so as to reflect more accurately the score that would have been observed had it been recorded at the scheduled time. With the exception of the 1-5 minute PPT evaluations, time windows will be created for each of the 5-minute scheduled PPT time points, the widths being ± 3 minutes. The time window for the 1-5 minute PPT evaluations will be ± 30 seconds.

- If an assessment is performed within a time point window, the corresponding value will be assigned to that time point (*e.g.*, an assessment performed anywhere between 3 and 7 minutes from the previous evaluation, regardless of when it was scheduled, will be assigned to the scheduled 5 minute time point).

If a particular time point has no value within its window, then the PPT or QST Heat value will be assigned using either Last Observation Carried Forward (LOCF) or Next Observation Carried Backward (NOCB). In particular, LOCF will be used for missing data prior to onset, and NOCB will be used for missing data after onset to conservatively estimate both onset and duration.

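### Primary mITT membership depends on the co-primary outcome, sessions without onset have no stated duration, and the synopsis and Section 9 differ on what a stop ends

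*Combined protocol and SAP*

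**What the plan says.** Below, A is one spray of the combination and CB one spray of benzocaine alone.

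- **Primary set.** Besides meeting the entry criteria, an mITT subject must have "either completed the two 60 minute test sessions or returned to baseline values in all the evaluation tests" (Section 13.2). The primary analyses use mITT. Of the ITT set the section says: "All secondary efficacy analyses and summaries will be performed using this population". No ITT analysis of the primary endpoint is stated.
- **Endpoint.** "Duration of effect is defined as the time (in minutes) from onset to treatment failure" (Section 13.5), for pin prick (PPT) and heat (QST). On early leavers: "For those discontinuing from the study for any other reason, the time to treatment failure will be censored at the last assessment time". On the test: "Pairwise comparisons for time-to-event related variables will be analyzed via a log rank model with treatment effects".
- **Discontinued subjects.** Section 11.7 puts their efficacy data in ITT but keeps them out of an evaluable-subject analysis, a set that Section 13.2 does not define.
- **No onset by 10 minutes.** Section 9: "the subject will be considered a treatment failure and no further assessments will be made". The synopsis also calls this a treatment failure.
- **Loss of effect at two consecutive visits.** The synopsis ends the test concerned; Section 9 ends the session.
- **Empty time points.** Section 13.4.1 uses LOCF before onset, and "NOCB will be used for missing data after onset to conservatively estimate both onset and duration".

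**The concern.** For PPT, Appendix 1A equates failure with full offset: "while a report of similar/more indicates complete regression of analgesia". For QST, the synopsis defines failure as a mean temperature at or below Baseline. Returning to baseline is therefore the endpoint event, and it also admits a non-completer to the primary set. Anyone who leaves while still numb is removed, so the Section 13.5 censoring rule has little left to act on.

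The clause does not say whether it applies by session or by subject. That matters because a session stopped by rule has not run for 60 minutes. A subject who regresses early on CB and is still numb at 60 minutes on A has, literally, neither completed both sessions nor returned to baseline on all tests. That is the pattern the trial hopes to see.

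Separately, a no-onset session is a failure without a start time, so its duration could be scored 0 or left out. The two stop rules also leave unclear whether one co-primary test can cut off the other.

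**Working it through.** **Inputs.** From the documents: 38 subjects per A regimen (synopsis), both tests every 5 minutes from 5 to 60 minutes, and a stop after two consecutive visits without effect. Section 13.1 gives no effect size, SD, dropout or no-onset rate, so there is no plan figure to reproduce. Assumed: median duration 40 min (A) and 20 min (CB) on both tests, onset at 5 min, exponential or Weibull (shape 2) durations, read at the next 5-minute visit and capped at 55 min. QST failure follows the synopsis; Section 13.5 words the QST condition in the opposite direction, which also needs correcting.

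**Step 1: difference with nobody removed.** Mean = 5 × Σ S(5k), k = 0 to 10, with S(t) = exp[−ln 2 · (t/median)^shape].
- Exponential: 37.02 − 26.75 = 10.3 min.
- Weibull: 39.89 − 23.75 = 16.1 min.

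**Step 2: clause read by subject, no dropout.** A session stops before 60 minutes if durations are 45 min or less. A subject is numb at 60 minutes if a duration exceeds 55 min. The case that can be done by hand is exponential, PPT and QST in full agreement, sessions independent:
- S_A(45) = 0.459, S_A(55) = 0.386, S_CB(45) = 0.210, S_CB(55) = 0.149.
- Numb on A, CB stopped: 0.386 × (1 − 0.210) = 0.305. Mean difference in this group: 55 − 19.45 = 35.55 min.
- Numb on CB, A stopped: 0.149 × (1 − 0.459) = 0.080. Mean difference: 22.14 − 55 = −32.86 min.
- Lost: 0.305 + 0.080 = 0.385, leaving about 23 of 38.
- Difference among those kept: (10.26 − 0.305 × 35.55 + 0.080 × 32.86) / 0.615 = 3.4 min.

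Simulation over PPT–QST correlations from 0 to 1 and both duration shapes, sessions independent:
- 26–47% of subjects lost, about 20–28 of 38 kept.
- Lost as numb on A and regressed on CB: 26–44%. The reverse: 0.3–9%.
- PPT difference: 10.3 falls to about 2.5–4.1 min (exponential); 16.1 falls to about 9.1–10.6 min (Weibull).

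Positive correlation between a subject's two sessions makes the fall smaller but does not remove it. A second set of assumptions (gamma durations with a shared subject effect, mean 15 min on CB, 5% no onset on each treatment counted as returned and scored 0, no withdrawal) gives 7.7 falling to 5.4 min for a mean of 25 min on A, and 16.0 falling to 10.1 min for 40 min.

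**Step 3: clause read session by session.** Rule-stopped sessions count as complete, and only true early leavers are sorted by outcome.

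| Assumed sessions left early | Shift in PPT difference (min) |
|---|---|
| 10% on each | −0.2 to +0.1 |
| 20% on each | −0.4 to +0.2 |
| A 20%, CB 5% | −1.2 to −0.2 |
| A 5%, CB 20% | +0.1 to +1.0 |

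All dosed subjects with Section 13.5 censoring: within 0.01 min of the truth in every case, provided leaving is unrelated to remaining numbness.

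**Step 4: no-onset sessions.** With a share f without onset, scoring 0 gives (1 − f_A) × mean_A − (1 − f_CB) × mean_CB.

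| Assumed no-onset | Exponential (min) | Weibull (min) |
|---|---|---|
| Excluded | 10.3 | 16.1 |
| 10% on both, scored 0 | 9.2 | 14.5 |
| A 20%, CB 5%, scored 0 | 4.2 | 9.3 |
| A 5%, CB 20%, scored 0 | 13.8 | 18.9 |

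If durations after onset are equal, scoring 0 raises log-rank rejection from 5% to 12–13% at 20% against 5% no-onset, because the score mixes onset with duration.

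**Step 5: time points after a stop.** The earliest stop after onset (10 and 15 minutes) leaves the nine visits from 20 to 60 minutes empty. NOCB has no later value to carry back. This touches only the responder percentages, which are secondary. After a no-onset stop, LOCF arguably supplies a non-responder value.

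**The case against.** The clause has an ordinary purpose: it keeps subjects whose testing ended by rule once the effect had gone. On that reading, balanced leaving moves the difference by at most 0.4 min against a 5-minute visit grid, and nothing in the protocol suggests 20% against 5% leaving in single-dose, 60-minute sessions in healthy volunteers. This stands, but the text does not settle which reading applies.

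Onset failure has its own comparisons in the synopsis and Section 8.3.2, which points towards measuring duration among sessions with onset. That is a fair indication, not a rule, because the same sessions are also labelled failures.

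Three stronger inferences are tempting, and the documents do not support them:
- A reader might infer that subjects stopped at the Session 2 Baseline are also sorted by their Session 1 outcome. Section 11.7 keeps discontinued subjects out of the evaluable analysis. If that means mITT, all of them leave whatever Session 1 showed. It is also unclear that someone with no Session 2 tests meets either limb. The supportable point is that Sections 11.7 and 13.2 do not agree.
- A reader might infer that Section 9 would cut off a co-primary test in 76–80% of subjects (the assumed case at PPT–QST correlation 0.5). That requires one regressed test to end the session, the reading least consistent with the synopsis. If both tests must have regressed, nothing is lost.
- A reader might infer that no time point after any stop has a value. The gap is limited to stops after onset, and Appendices 1A and 2 already point to non-responder.

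Making ITT primary in a proof-of-concept study is partly a matter of preference. However, Section 13.6 declares success if either endpoint is significant, so an unstated rule could decide the result.

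**Conclusion.** The concern holds in the text, whatever rates are assumed. Primary-set membership of non-completers depends on the co-primary outcome, Section 11.7 does not agree with Section 13.2, no-onset sessions have no duration, and the two stop rules differ.

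The size depends on the reading. Session by session, the mITT effect is small. By subject, it removes 26–47% of subjects and takes away most of the PPT difference (exponential) or over a third of it (Weibull), against A. The documents do not establish that the by-subject reading is intended, so that loss is a risk of the wording, not a forecast. The no-onset rule moves the difference by several minutes only if onset rates differ. All medians, rates, correlations and duration shapes are assumptions, so the direction of any bias in the actual trial is unknown. The coding of visits after a post-onset stop is a clarification only.

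**What to change.** 1. Run both co-primary analyses on the ITT set of Section 13.2, censoring at the last assessment as Section 13.5 provides. State that a session stopped by rule counts as complete. Keep mITT as a sensitivity analysis, and reconcile Section 11.7 with Section 13.2.
2. Before unblinding, fix one primary rule for sessions without onset. Report the result both with duration 0 as an event and among sessions with onset, noting that the first mixes onset and duration.
3. Reconcile the synopsis and Section 9 on whether a stop for one test ends the other.
4. As a clarification, code visits after the post-onset two-failure stop as non-responder, with the ITT denominator.

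Cost: a protocol amendment with sponsor and IRB approval under Section 14.5, and some programming. No added subjects, visits or data.
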